7 STATISTICAL ANALYSIS FOR PRIMARY OBJECTIVES

7.1 Structure of the Analysis Approach for Assessing Vaccine Efficacy and Relative Vaccine Efficacy

We first consider the following three issues that require attention across the primary and exploratory objectives:

1. Hierarchy of analyses and false-positive control/multiplicity adjustment
2. Adjustment for baseline covariates
3. Antimalarial treatment

For issue 1, as structured in Tables 2, 3, 4, the three sets of comparison types are (1) comparisons of active vaccine study groups vs. rabies control; (2) comparisons of novel active vaccine study groups vs. the standard RTS,S/AS01E regimen; and (3) comparisons of novel active vaccine study groups. Comparisons of Group 4 vs. Group 1 and of Group 5 vs. Group 1 are of primary interest and will not be adjusted for multiplicity in either cohort or for any time period of follow-up.

For all remaining comparisons, the multiplicity adjustment approach for primary objective analyses is as follows: For comparisons of type (1) (remaining comparisons minus the two primary ones), (2) and (3) separately, for each cohort (ATP and TVC) and time-period of follow-up separately, q -values controlling the false discovery rate

(calculated using the *p.adjust* function in R) and Holm-adjusted p-values controlling the familywise type 1 error rate will be computed along with unadjusted p-values for the set of multiple comparisons. Results are expected to be correlated across cohorts and follow-up periods, such that full FWER adjustment is deemed overly stringent on type I error control at the expense of reduced power.

For issue 2, methods based on targeted maximum likelihood will use Super Learner as an intermediate step, both for predicting the probability of a missing measurement of primary endpoint 2 and for predicting the value of primary endpoint 2, allowing the entire set of pre-specified baseline covariates to potentially be used in predictions (see Section 7.6.1 for definition of an observed/known primary endpoint 2). In contrast, methods not using targeted maximum likelihood (e.g., Cox proportional hazards models) will instead stratify by study site in the study site-pooled analysis and possibly adjust for the “ATP Propensity Score” univariate baseline covariate defined below in Section 7.5 if this propensity score is found to be sufficiently predictive of the outcome under study.

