Vaccine efficacy against primary endpoint 2 for a given vaccine arm vs. the control arm will be assessed by the additive difference in the mean number of new molecularly confirmed malaria infections in each vaccine arm vs. the mean number of new molecularly confirmed malaria infections in the control vaccine arm. The targeted maximum likelihood estimator of Porter et al. (2011) will be used, which incorporates information in baseline study characteristics predictive of whether data are missing or predictive of the number of new molecularly confirmed malaria infections. This method also provides a way to estimate the variance of the estimated mean number of new molecularly confirmed malaria infections in each study arm. Based on these variance estimates, Wald tests will be used to test for the additive difference VE differing from zero and to obtain a 95% CI. These analyses are done for each comparison specified in Tables 2–4 with the control group as the comparison arm.

Similarly, the same methods will be used to test for differences in the mean numbers of new molecularly confirmed malaria infections between vaccine arms, and to compute 95% CI for these differences. Again Wald 95% CIs and Wald 2-sided p-values are used. These analyses are done for each comparison specified in Tables 2–4.

7.6.1 Handling of Loss to Follow-up and Missing Visit Data for Primary Endpoint 2

The number of new molecularly confirmed malaria infections must be estimated based on the genotyping/haplotyping data, and we use an operational definition for what data availability constitutes enough information for the study endpoint to be considered observed/known for an individual. A participant's endpoint is considered to be observed/known if both (a) s/he had at least one visit with genotyping data in the 75-day period leading up to the last scheduled visit in the given follow-up period (e.g., Month 0 to 20, Month 2.5 to 14, Month 7.5 to 19), and (b) s/he had genotyping data from at least 50% of scheduled visits during the given follow-up period. If the last scheduled visit in the given follow-up period was missed, then the 75-day period is keyed off of the target date of the missed visit. The premise for this estimator is that, with these available data, it will be possible to accurately estimate the number of new molecularly confirmed malaria infections during the follow-up period.

TMLE inference about reverse cumulative distribution functions (RCDFs)

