The TMLE of the RCDF incorporates both a Super Learner estimate of the probability of missing the outcome conditional on baseline covariates and a Super Learner estimate of the outcome itself conditional on baseline covariates (again done with the *SuperLearner* or *sl3* R packages with default learners and baseline covariates described in Section 6.2). The method is well-suited to the application, because some participants who do not have an observed primary endpoint 2 due to not meeting condition (a) or (b) in the paragraph above will still have useful data (e.g., genotyping

results on, say, 40% of samples) for predicting primary endpoint 2, and any prediction ability even if quite imperfect improves efficiency of the analysis. More specifically, we view the objective of inference about the mean of primary endpoint 2 as a problem to address using two phases of data—phase one data measured in all participants and the phase two data the primary endpoint 2 (Y) that is missing for some participants. The phase one data include baseline characteristics of participants as well as auxiliary outcomes that may be predictive of the outcome Y of interest. Accounting for these phase one data, including information from participants with Y missing, can improve robustness and efficiency. We select as a phase one auxiliary outcome of interest (call it Y^*) the number of molecularly detected new infections divided by the number of available molecular detection tests during the time period of study for a given analysis. If a participant has zero in the denominator, then Y^* is set to 0. Moreover, the method is doubly-robust such that it gives valid inferences even if the Super Learner model for this prediction is inconsistent, as long as the probability of missing the outcome conditional on baseline covariates is consistently estimated. Thus, importantly, a completely accurate prediction is not required for valid inference, a property that has been shown theoretically and in simulation studies in many TMLE papers.

TMLE inference on mean number of new malaria infections and study group contrasts will be reported. Missing data for this TMLE are handled in the same way as described above for the TMLE of the RCDF.

7.7 Assessment and Comparison of Vaccine Efficacy after the Month 14 or 20 Boost through to Month 32

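### Endpoint 2 TMLE: coding Y* as 0 for a child with no molecular test treats that child as having no new infection, and the SAP does not say which model uses Y*

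*SAP*

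**What the plan says.** SAP 7.6.1 treats endpoint 2 (Y) as known only if a child has a genotyped visit in the last 75 days of the window and "s/he had genotyping data from at least 50% of scheduled visits during the given follow-up period". Otherwise Y is missing. A child with no test therefore always has Y missing.

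The TMLE combines a model for the probability that Y is missing with "a Super Learner estimate of the outcome itself conditional on baseline covariates". SAP 7.1 likewise describes Super Learner as "allowing the entire set of pre-specified baseline covariates to potentially be used in predictions". Section 7.6.1 then sets up a two-phase problem with "phase one data measured in all participants". It selects Y* as a phase-one auxiliary outcome and fixes its value when there are no tests: "If a participant has zero in the denominator, then Y^* is set to 0". The motive is that "any prediction ability even if quite imperfect improves efficiency of the analysis". No sentence says whether Y* goes into the outcome model, the missingness model, both or neither.

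Validity is said to hold even with a poor outcome prediction, "as long as the probability of missing the outcome conditional on baseline covariates is consistently estimated". The mean contrasts follow suit: "Missing data for this TMLE are handled in the same way as described above for the TMLE of the RCDF".

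**The concern.** For a child with no test, the 0 is a filler and not a measurement. Among children whose Y is observed, Y* = 0 occurs exactly when no new infection was counted, so Y = 0. (This includes a child carrying only a persisting haplotype.) A model that learns from those children and is applied to a never-tested child will predict about zero infections, whatever that child's baseline risk.

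The section covers the RCDFs and the mean contrasts for endpoint 2, including Group 4 and Group 5 versus control, which SAP 7.8 tests without multiplicity adjustment. Because the use of Y* is not specified, two programmers following the SAP could obtain different endpoint 2 estimates whenever never-tested children are present.

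**Working it through.** The documents state no untested share, no expected mean count and no power for endpoint 2, so there is no figure to reproduce. All shares and means below are assumptions.

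**1. Why double robustness does not help.** Let D = 1 if Y is observed, W the baseline covariates, g(W) = P(D = 1 | W) correctly modelled, and Q the outcome model using W and Y*. Suppose Y is missing at random given W. The estimator then has bias

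E[(1 − g(W)) × {E(Q | D = 0, W) − E(Q | D = 1, W)}].

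If the children with D = 0 are the never-tested ones, Q is about 0 for them and averages the true mean for the others. The bias is then −(untested share) × (mean count of the untested children). It does not vanish when g(W) is correct, because the coded Y* is itself determined by missingness. If Y* is in a flexible missingness model, the estimator converges to E[E(Y | D = 1, W, Y*)], which again gives the untested child about 0.

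**2. Arm mean and RCDF.** If untested children have the arm's mean μ, the result is (1 − p)μ. With μ = 3 and p = 5%: 0.95 × 3 = 2.85, a bias of −0.15. An RCDF point of 0.90 becomes 0.95 × 0.90 = 0.855.

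**3. Additive difference.** The result is (1 − p_v)μ_v − (1 − p_c)μ_c. With means 2 (vaccine) and 3 (control), the true difference is −1.
- 5% in both arms: 1.90 − 2.85 = −0.95.
- 2% vaccine, 8% control: 1.96 − 2.76 = −0.80.
- 8% vaccine, 2% control: 1.84 − 2.94 = −1.10.

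Equal shares shrink the difference by p. Unequal shares can move it either way.

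**4. Large-sample TMLE simulation.** Assumptions: 20 monthly tests, mean about 1 or 2.7 new infections, missingness dependent on site only, 0 or 5% of children partly tested, 200,000 children per cell. Relative bias of the arm mean:

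| Untested | Y* in outcome model | Y* in missingness model only |
|---|---|---|
| 2% | −2.1 to −2.3% | −2.0 to −2.2% |
| 5% | −5.3 to −5.4% | −5.1 to −5.4% |
| 10% | −10.7 to −10.9% | −10.1 to −10.8% |

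At 0% untested the bias is at most 0.2% in every variant, so the filler is the cause. With Y* in neither model it stays within 0.3%. With untested children predicted from baseline covariates alone it stays within about 0.15%.

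**5. Dependence on the learner.** A second simulation used an AIPW estimator in place of the TMLE, 12 visits, and arm means from 1 to 9. At a 5% share:
- Linear or binned outcome model: bias of 1.03 to 1.08 times the share.
- Logistic missingness model only: 0.46 to 1.02 times the share, smaller when few tested children have a zero count.
- Log-link outcome model: untested children shift the mean by −0.57 to −0.81 times the share. That learner is already biased by +0.4% to +18% with nobody untested, so the net sign varies.

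**6. Effect on inference.** Same AIPW set-up, 250 per arm (the parent trial's evaluable number in Protocol 6.2), means 4.2 and 2.9, true difference −1.30, Y* in a linear outcome model:
- 5% untested in both arms: −1.24 with the zero rule (coverage 94%), −1.30 with the fix (95%). The shift of 0.06 is about 0.2 of the standard error (0.06 / 0.286).
- 10% in both arms: −1.16 (91%) against −1.30 (95%).
- Rejection under no effect at 5% in both arms: 0.057 against 0.060. Power at a true difference of about −0.60: 49% against 51%.

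**The case against.** **The wording on model inputs names baseline covariates only.** SAP 7.1, 7.6 and 7.6.1 all describe the models that way, and on that literal reading Y* is in neither model and the bias is nil. This stands as a possible reading. But Y* would then have no function in a paragraph that selects it to help predict Y and writes a rule for its zero denominator.

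**Never-tested children may not be in the ATP analyses.** SAP 3 requires children to be observed at risk 14 days after Dose 3 and uses one ATP cohort for both endpoints. For endpoint 1, SAP 7.5.1 censors at the last parasite-negative sample in the window, a date that a child without a sample does not have. Section 3 does not explicitly demand a test, so this is unsettled, but it is a fair reason to expect few or none.

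**A zero denominator is hard to reach.** It needs no usable scheduled or unscheduled sample in the window. The 12-month ATP windows hold 12 monthly visits (Months 3–14 or 8–19). SAP 5.2 also expects about 14,400 clinical samples in 20 months, or 14,400 / 1,500 = 9.6 per child. In the TVC, 31,500 / 1,500 = 21 monthly samples matches Months 0–20 with enrolment included. If the enrolment sample counts as a test, the denominator is at least 1. This limits how often the quoted rule applies. It does not remove the problem: a child with only the enrolment sample then gets 0/1 = 0, since SAP 5.1.1 never counts enrolment infections as new.

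**A reader might infer a large share from SAP 8.5.1**, where 25.4% of children are censored under the definition of four consecutive missed visits. That figure covers gaps starting at any time, including late ones in children with many tests. It is not evidence about children with none.

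**Conclusion.** The zero rule is a stated rule that misleads under conditions the SAP leaves open. If never-tested children are analysed and Y* enters a nuisance model, the arm mean and RCDF are generally too low. The bias is roughly the untested share with Y* in a linear outcome model, and about 0.5 to 1.1 times it with Y* in the missingness model only, across the settings tried. It would be nil if the untested children truly had no new infections, and other model errors could offset it. The most plausible place for such children is early dropout in the TVC.

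With equal shares the consequence for the contrast is modest: attenuation by about the share, with little change to the test. A reader might infer that the endpoint 2 results are known to be biased, or that false positives are inflated. The documents support neither. A stress case with 8% untested in control and 1% in vaccine does give 17% rejection under no effect. Nothing in the documents indicates that shares differ, or that they are that large.

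Confidence in the mechanism is high; the size in this trial is unknown. The calculations assume missingness at random given baseline covariates and use simple learners in place of a full Super Learner library.

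**What to change.** In SAP 7.6.1:

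1. Name the nuisance model(s) that use Y*.
2. Replace the zero rule with: *Y\* is defined only for participants with at least one post-enrolment molecular test (scheduled or unscheduled) in the window; for participants with none, Y is predicted from baseline covariates alone.* In practice, model having any test on baseline covariates. Then, among tested children, model both the observation of Y and Y itself on baseline covariates plus Y*. Leaving Y* out of both models is a simpler alternative that also removes the bias. Adding only a no-test indicator does not work, because Y is missing for every such child.
3. Tabulate never-tested children by arm, cohort and window. SAP 7.3 tabulates lost samples, not children without any test. If every count is zero, nothing needs rerunning.
4. If any count is non-zero and Y* was used, report the corrected estimate beside the original, labelled post hoc. SAP 5.1.1.1 and 9.3 show that Month 20 data and results had been seen before version 1.7.

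The cost is a count table, a few sentences and some coding on existing data. Intervals widen slightly (empirical standard error 0.291 against 0.286 at an assumed 5% untested in both arms). The corrected estimator still assumes that never-tested children are missing at random given baseline covariates.

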7.8 Significance Level

In primary analyses comparing Group 4 vs. Group 1 and Group 5 vs. Group 1 in either study cohort and for any time period of follow-up, statistical significance is defined as an unadjusted p-value ≤ 0.05 . In all remaining primary analyses, multiple hypothesis testing adjustment is used, as described in Section 7.1., to evaluate statistical significance. Within each multiple comparison procedure, statistical significance is defined as a q-value ≤ 0.2 or a Holm-Bonferroni-adjusted p-value ≤ 0.05 , together with an unadjusted p-value ≤ 0.05 . All statistical tests in support of the primary objectives are two-sided.

7.9 Interim Analyses

An interim genetic analysis will occur on data collected up to Month 21 as per the main MALARIA-094 protocol. A second analysis will be performed on data collected up to Month 32. These analyses will be triggered by the last enrolled participant reaching Month 21 or Month 32, respectively. A study report presenting all results accounting for study follow-up through to Month 32 will be produced.

All genetic material and sequence analyses will be performed through the study periods following a schedule agreed-upon by GSK and as specified in this SAP. At the interim analyses, the TVC and ATP cohort analyses will be performed using data through Month 20, with comparisons and follow-up periods defined in Tables 1, 2, and 3. At the final analysis, the TVC and ATP cohort analyses will also analyze new malaria infection data through Month 32, with comparisons and follow-up periods defined in Table 4.

7.10 Procedures for Preventing Biases and Accounting for Missing, Unused, or Spurious Data

Bias in genotyping analyses will be prevented by the sample collection protocol previously described and procedures specified in the main trial protocol MALARIA-094 that will de-identify subject samples. Comparisons of relative diversity between vaccinated and control vaccinated arms will be made at the level of subject study sites when possible. In all cases, adjustments by study sites will be performed. To prevent differential misclassification bias, sequence analysis is performed blinded with respect to knowledge about the vaccination status connected to an isolate and to the specific malaria outcome (i.e., asymptomatic infection or clinical malaria).

The genotyping and re-sequencing platforms at the Broad Institute implement strict quality control guidelines to reduce the likelihood of sample contamination. Appropriate and rigorous data cleaning for all single nucleotide polymorphisms (SNPs) will be performed. Unreliable sequencing or genotyping data will be excluded from the analysis, and reasons for excluding data included in the data base when available. All unused or discarded samples will be noted and reported as described in the main trial protocol MALARIA-094.

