### **6.1. Analytical Plan**

A formal Statistical Analysis Plan (SAP) will be finalized and approved by all parties prior to data un-blinding. All genetic material and sequence analysis will be performed through the study period in a schedule agreed upon by GSK.

Briefly, an alpha level of 0.05 will be used to test statistical significance. All statistical tests will be two-sided. Baseline characteristics of interest will be summarized by the appropriate comparison group. The number of filter paper samples lost or not collected will also be tabulated by comparison groups, as well as PCR negative results or any other reason for excluding a sample from the analysis. In mixed infections, it is expected that sequencing will yield the genotype of the more prevalent strain(s) or a heterozygous call. All analyses across study sites will be adjusted for study site. Analysis stratified by study site will also be presented.

*Primary Endpoint 1.* Instantaneous VE against the first new malaria infection endpoint observed during 12 months after the third immunization in each vaccine arm vs. the common control vaccine arm will be assessed using a proportional hazards model with vaccine group indicator as the lone covariate, with the model stratified by study site (i.e., allowing a separate unknown baseline hazard of the first new malaria infection at each study site). The same proportional hazards modeling approach will be used for comparing the hazard of the first new malaria infection between pairs of vaccine arms, except hazard ratios will be assessed instead of VE parameters. A secondary analysis of the first new malaria infection endpoint will estimate instantaneous VE over time for each vaccine arm versus the control vaccine arm using nonparametric kernel smoothing with pointwise and simultaneous confidence bands [Gilbert et al., 2002] and using flexible partial-likelihood based proportional hazards modeling, for example using time-varying coefficients in the Cox model modeled with smoothing splines or using smoothed Schoenfeld residuals [Durham et al., 1998].

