“The cumulative distribution functions will be estimated in two ways: first, by stratifying by study site using the Kaplan-Meier estimator, and second, by adjusting for other baseline participant characteristics via targeted maximum likelihood estimation (TMLE, Moore and van der Laan, 2009).”

as

“The cumulative distribution functions will be estimated in two ways: first, by using the Nelson-Aalen estimator for the cumulative hazard function, and

second, by adjusting for other baseline participant characteristics via targeted maximum likelihood estimation (TMLE, Moore and van der Laan, 2009)."

The Kaplan-Meier estimator was replaced with the Nelson-Aalen estimator because the simultaneous confidence band program is available for the Nelson-Aalen estimator only. This program does not accommodate stratification, therefore an unstratified estimator is considered, which matches the kernel-smoothed estimation of instantaneous hazard functions and their contrasts, which is also unstratified.

- Section 7.5: In the last paragraph, revised the sentence

"These analyses will be done for each individual and pair of study groups specified in Tables 2, 3, and 4, except the analyses comparing active vaccine study groups and using the control group for bias-correction from possible secular trends will not be done (i.e., comparisons denoted by asterisks in Tables 2, 3, 4)."

as

"These analyses will be done for each individual and pair of study groups specified in Table 5, analogously to the analysis of instantaneous kernel-smoothed hazard functions and their contrasts."

Date: April 4, 2022

SAP version: 1.2

Modifications:

- Added Section 9 on post-hoc exploratory analyses.

Date: October 24, 2022

SAP version: 1.3

Modifications:

- Added Section 5.1.1.1 describing the modified post-hoc definition of molecular parasite positivity for application in Month 32 analyses.
- Added the statement

"All analyses using follow-up through Month 32 will use the modified post-hoc definition of molecular parasite positivity as described in Section 5.1.1.1."

at the beginning of Section 7.7 to reiterate the difference in the SAP-specified

read threshold for molecular parasite positivity in analyses through Month 20 vs. Month 32 of follow-up.

Date: March 8, 2023

SAP version: 1.4

Modifications:

- Added Section 9.1 on sensitivity of overall VE estimates to the read count threshold for parasite positivity.

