The TVC analyses directly compare hazard rates between vaccine arms not including control group data, as do the ATP analyses that compare vaccine arms within the same vaccination schedule (Month 0, 1, 2 or Month 0, 1, 7). In contrast, ATP analyses comparing vaccine arms with a Month 0, 1, 2 schedule, versus the Group 5 vaccine arm with a Month 0, 1, 7 schedule, include the control vaccine group data in each distinct follow-up period between vaccinations, to control for potential bias due to secular trends, for example caused by seasonality of malaria infection. In particular, the ATP analyses that make an adjustment via the control group are listed in Tables 2, 3 and 4 in Section 5.1.

For example, as in Table 2, the analyses are done using a Month 2.5 to 14 follow-up period for Groups 3 and 4 versus a Month 7.5 to 19 follow-up period for Group 5, creating the same amount of follow-up for malaria post-Dose 3 in the groups being compared.

We implement these analyses using the Cox proportional hazards model as follows: To assess relative VE comparing GP5 with GP2+GP3 in the ATP cohort during 11.5 months following the third dose in each regimen, we will fit (1) a Cox model to GP5 and GP1 data during months 7.5–19 of follow-up, and (2) a separate Cox model to GP2+GP3 and GP1 data during months 2.5–14 of follow-up. We will estimate the hazard ratio comparing GP5 months 7.5–19 with GP2+GP3 months 2.5–14 as the ratio of the estimated GP5-vs-GP1 hazard ratio in model (1) and the estimated GP2+GP3-vs-GP1 hazard ratio in model (2). We will use a nonparametric bootstrap procedure to construct a 95% CI for the GP5-vs-GP2+GP3 hazard ratio, as well as for obtaining a 2-sided p-value for the test of the null hypothesis that the hazard ratio equals one.

A secondary analysis will estimate instantaneous VE over time for each vaccine arm versus the control vaccine using nonparametric kernel smoothing (Gilbert et al., 2002). This analysis will provide pointwise and simultaneous 95% CIs about instantaneous VE over time, together with a p-value for whether instantaneous VE varies with time. Similarly, we will apply this method to estimate hazard ratios over time comparing pairs of vaccine arms. Nonparametric kernel smoothing will also be used to estimate the instantaneous risk of new malaria infection over time for each individual study arm, where this plot for the control vaccine arm is useful for displaying background malaria exposure and infection intensity over time.

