An additional secondary analysis will estimate cumulative distributions of the time to the first molecular detection of a new malaria infection by study group. The cumulative distribution functions will be estimated in two ways: first, by using the Nelson-Aalen estimator for the cumulative hazard function, and second, by adjusting for other baseline participant characteristics via targeted maximum likelihood estimation (TMLE, Moore and van der Laan, 2009). The latter fully covariate-adjusted method is especially relevant for the ATP analysis, as described above. This analysis uses as an intermediate step an estimate of the distribution of the time to the first molecular detection of a new malaria infection conditional on baseline covariates (listed in Section 6.2), which is produced using the Super Learner method (as implemented in R packages *SuperLearner* or *s3*). Given the possibility of our requiring resampling methods (e.g., nonparametric bootstrapping) to obtain inference, we may restrict the Super Learner library of candidate regression methods to those that are computationally stable and run relatively quickly. For example, these candidate regressions will include regressions based on several different generalized linear models that include up to two-way interactions between covariates and treatment.

The estimated cumulative distribution functions of the time to the first molecular detection of a new malaria infection will be plotted with 95% pointwise and simultaneous

confidence intervals, through to the last time point in the specified time period. Similarly, point estimates and 95% confidence intervals will be produced for additive differences and cumulative incidence-based vaccine efficacy or cumulative relative risk contrasts between the two study groups being compared. These analyses will be done for each individual and pair of study groups specified in Table 5, analogously to the analysis of instantaneous kernel-smoothed hazard functions and their contrasts.

7.5.1 Handling of Loss to Follow-up for Primary Endpoint 1

Cox proportional hazards models and nonparametric inference on instantaneous hazard ratios over time

Regarding loss to follow-up, for both TVC and ATP cohort analyses, for each participant included in the analysis, the right-censoring time is defined as the last parasite negative sample collection date recorded during the follow-up period under study. The assumption of random censoring is needed for valid inferences.

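### The pooled kernel estimate of VE over time and its time-variation p-value ignore study site, against the protocol's site rule; if site transmission differs by about 3:1 or more, a constant VE can appear to vary with time

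*SAP*

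**What the plan says.** The general rule is in Protocol 6.1: "All analyses across study sites will be adjusted for study site". The next sentence adds: "Analysis stratified by study site will also be presented". SAP 7.10 has a similar line, "In all cases, adjustments by study sites will be performed", but it directly follows a sentence about comparing parasite diversity between arms, so it may be meant more narrowly. The protocol sentence carries the point without it.

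SAP 7.5 follows the rule for the main analysis of primary endpoint 1: the Cox model has a separate baseline hazard for each site. The same section then plans a secondary kernel-smoothed estimate of instantaneous VE, with confidence bands, "together with a p-value for whether instantaneous VE varies with time". Neither that paragraph nor Table 5 contains a site term. The version 1.1 entry in the modification history explains why the Nelson-Aalen curves lost their stratification: "therefore an unstratified estimator is considered, which matches the kernel-smoothed estimation of instantaneous hazard functions and their contrasts, which is also unstratified". The software limit is given as the reason for the Nelson-Aalen choice. For the kernel analysis the entry only records that it was already unstratified.

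Protocol 6.1 paired kernel smoothing with flexible partial-likelihood modelling and named time-varying Cox coefficients and smoothed Schoenfeld residuals as examples. SAP 7.5 keeps only the kernel method, so the kernel p-value is the only test of time-varying VE specified there.

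**The concern.** Suppose the vaccine cuts the hazard by the same fraction at both sites at all times, but transmission is higher at one site. Control children at that site have their first infection sooner than vaccinated children there, so they leave the risk set sooner. As follow-up continues, the remaining controls come increasingly from the low-transmission site, and the remaining vaccinees less so. The pooled hazard ratio moves away from its within-site value although VE has not changed at either site. Randomization balances site at time zero but not among children still uninfected months later.

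The plan makes this plausible. The Cox model already allows the site hazards to differ. SAP 7.7.1 foresees that the majority of children will have been infected by Month 20, so depletion will be heavy. Enrolment began about seven months apart at the two sites (October 2017 and May 2018, SAP 1), so a given follow-up month falls in different calendar seasons.

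At stake is how a small p-value for time-varying VE is read. Durability is a stated interest (SAP 5.1.6), and a shift in site mix could be taken for a property of the vaccine.

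**Working it through.** The documents give no figure for this point, so there is none to reproduce.

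**Inputs from the documents.** About 300 children per arm (SAP 2). Kernel contrasts are one arm against another, with no pooling of Groups 2 and 3 (Table 5). The ATP window is Month 2.5 to 20, which is 17.5 months, for Groups 2 to 4. Tests are two-sided at 0.05 (Protocol 6.1).

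**Assumptions.** A 50:50 site split, constant within-site VE, and the site hazards shown below.

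**Step 1: pooled VE over time.** Let h_s be the control hazard at site s and θ the common hazard ratio. With equal site weights and constant hazards:

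- control: H_C(t) = Σ h_s exp(−h_s t) / Σ exp(−h_s t)
- vaccine: H_V(t) = θ Σ h_s exp(−θ h_s t) / Σ exp(−θ h_s t)
- pooled VE(t) = 1 − H_V(t)/H_C(t)

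Worked case: θ = 0.6 (true VE 40%), hazards 0.08 and 0.25 per month, t = 11.5.

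- Control survivors: exp(−0.92) = 0.3985 and exp(−2.875) = 0.0564. H_C = (0.08×0.3985 + 0.25×0.0564)/(0.3985 + 0.0564) = 0.1011.
- Vaccine survivors: exp(−0.552) = 0.5758 and exp(−1.725) = 0.1782. H_V = 0.6×(0.08×0.5758 + 0.25×0.1782)/(0.5758 + 0.1782) = 0.0721.
- VE = 1 − 0.0721/0.1011 = 28.7%.

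| Site hazards per month | Ratio | VE at start | VE at 11.5 months | VE at 17.5 months |
|---|---|---|---|---|
| 0.08 / 0.16 | 2:1 | 40% | 36.2% | 34.8% |
| 0.08 / 0.25 | 3.1:1 | 40% | 28.7% | 29.0% |
| 0.05 / 0.25 | 5:1 | 40% | 20.7% | 22.9% |

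The slight recovery in the last two rows occurs because few children from the high-transmission site remain at risk in either arm.

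**Step 2: seasons out of phase.** With an assumed 80% seasonal amplitude, peaks half a year apart between sites and annual hazards of 0.5 and 1.5, a constant VE of 50% appears anywhere from about 23% to 55% over follow-up. The distortion then runs in both directions.

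**Step 3: false-positive rate.** The kernel test was not simulated; two stand-ins were used, both at 300 vs 300 over 17.5 months with VE constant within site.

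The first compares early with late log hazard ratios (true VE 40%, cut at 4 or 8.75 months):

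| Site hazards per month | Unstratified | Site-stratified |
|---|---|---|
| 0.08 / 0.16 | about 5-7% | about 5% |
| 0.08 / 0.25 | about 7-9% | about 5% |
| 0.05 / 0.25 | about 10-16% | about 5% |

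The second is a Schoenfeld-residual score test (true VE 30% or 50%, dropout 0.08 per year, 2000 trials). Unstratified rejection was 5.0-5.4% with equal hazards, 5.3-6.0% for annual hazards of 1 vs 2, 7.2-11.3% for 1 vs 3, and 9.2-21.0% for 0.5 vs 2.5. Stratified rejection was 4.2-5.8% throughout. At the larger gaps nearly all the excess pointed towards waning.

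**The case against.** The strongest reply is that the SAP departs from the rule openly, in analyses it labels secondary, and that safeguards exist. The protocol promises site-stratified results, and the close of SAP 8.4.4 suggests that by-site analysis is general practice. This has weight: by-site kernel curves would expose the artefact. But SAP 7.5 does not specify them, and by-site curves alone would not correct the pooled p-value. The open note in the modification history also does not amend the protocol rule or say how the pooled curve should be read.

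A second reply is that the size rests on invented site rates. That stands. SAP 1 speaks only of moderate to high transmission. At 2:1 the curve drops about 4 to 5 points and the test is barely inflated. The kernel test's own error rate is also unknown.

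A third reply is that stratifying by site is not a complete cure. That stands too. With gamma frailty added within sites (assumed variance 0.5 to 1, hazards 0.08 vs 0.16), both the stratified and the unstratified tests reject in roughly 8-12% of trials. Depletion from within-site heterogeneity is a general limit of hazard-ratio waning tests.

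A reader might also infer that the unstratified Nelson-Aalen curves are wrong. The documents do not support that. Under randomization, with censoring unrelated to site, they estimate marginal cumulative incidence validly. SAP 7.5 adds a second version "by adjusting for other baseline participant characteristics via targeted maximum likelihood estimation", using the Section 6.2 covariates, the first of which is study site.

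**Conclusion.** The inconsistency is established from the text: the kernel VE analysis and its time-variation p-value pool two sites without adjustment, and the protocol rule carries no exception for them.

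The consequence is conditional. With site transmission differing by about 3:1 or more, a constant within-site VE of 40% would appear as about 29% or 21% at 11.5 months, and a nominal 5% test would reject in roughly 7-9% or 10-16% of trials. At 2:1 the effect is negligible. These figures rest on assumed hazards, an assumed even site split, constant hazards and stand-in tests.

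Two stronger readings are not supported. A reader might infer that the trial will report spurious waning. The documents give no site rates from which to conclude that, and with out-of-phase seasons the false pattern can go either way. A reader might also infer that the main efficacy result is compromised. It is not: the primary Cox VE is stratified by site, and the significance rules in SAP 7.8 do not depend on this secondary p-value.

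**What to change.** In SAP 7.5:

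- Base the time-variation p-value on a Cox model stratified by site, with a time-varying vaccine coefficient or scaled Schoenfeld residuals. Protocol 6.1 already names time-varying Cox methods as examples, although it does not specify a site-stratified version.
- Present kernel VE curves for each site beside the pooled curve.
- Label the pooled curve as marginal over sites, and state it as an exception to the Protocol 6.1 rule.
- Note that stratification removes the between-site artefact but not depletion from differences in risk among children within a site.

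The cost is SAP wording, modest programming and wider confidence bands for the by-site curves. No new data are needed, and the primary analysis does not change.
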